## 4 Protocol synopsis

### 4.1 Brief summary

The purpose of this study is to assess the feasibility of a smart phone application (app)-based intervention to reduce risks from wildfire smoke among young adults with asthma. We will pilot test two interventions, both based on the EPA's Smoke Sense phone app compared to a control group. We will recruit 60 young adults aged 18-26 with asthma and randomize them to 1 of 3 groups for a 3-month study period during wildfire season. The long-term goal is to minimize asthma exacerbations from exposure to wildfire smoke. Our aims are to:

1. Establish the feasibility (recruitment, enrollment, retention rates), acceptability (intervention engagement, fidelity, usability, research attitude), and barriers and facilitators of adopting the technology of the Smoke Sense interventions and use of portable devices in young adults with asthma.
2. Explore the preliminary impact of the Smoke Sense interventions on lung function and asthma control. These primary outcomes will be assessed using objective measures (spirometry) and validated, self-report tools. Secondary outcomes will be anxiety, exposure reduction behaviors (e.g. stayed indoors, wore a mask), and symptom mitigating behaviors (use of medication, unscheduled health care appointments), measured via self-report and a Global Positioning System device. Outcome by group will be summarized. Preliminary evidence of treatment effect and its variance will be examined for a future clinical trial.
3. Explore potential mediators (medication adherence, self-management skills, stress) and moderators (asthma severity/control) of the interventions to asthma outcomes.

### 4.2 Study design

#### 4.2.a. Narrative study description (of the protocol)

We propose an 8 week, 3-arm randomized clinical trial to pilot test two interventions, Smoke Sense and Smoke Sense Plus, in comparison to a control group among young adults with asthma. This research design enables an examination of feasibility and acceptability of processes that are key to the success of a future trial. The design also enables us to estimate the effect size of the Smoke Sense interventions on primary (lung function, asthma control, asthma quality of life) and secondary outcomes of interest (anxiety, exposure reduction behaviors, and symptom mitigating behaviors), as compared to a control group, among young adults with asthma. Measures will be assessed at baseline, 4 and 8 weeks. The intervention period is 8 weeks. The sample will consist of 60 young adults, 18-26, with diagnosed asthma (of any type). Study activities will take place during wildfire season, July-October. To be included in the study, participants will need to have been diagnosed by a health care provider as having asthma, own a smart phone (Android or iOS platforms), speak and read English, and reside in Spokane County, WA. People can not be in the study if they are a Smoke Sense app user, have had surgery within 3 weeks of enrollment, or a cardio-vascular condition, both of which are contraindications for spirometry.

The choice of sample size (n=60 participants) was based on achieving Aim 1, focusing on assessment of the feasibility and acceptability of the Smoke Sense interventions. *Feasibility.* We expect that the true consent rate of eligible young adults is 75%. To test this, we will recruit up to 86 eligible individuals. There is an 89% probability that 60 or more of these individuals will consent to participate if the true consent rate is 75% (based on the cumulative binomial probability). We expect that the true rate of completion of the week-8 assessment is 80%. If this is correct, there is an 87% probability that we will observe at least 45 out of 60 participants completing the week-8 assessment. Similarly, we expect that the true rate of completion of the week-8 assessment is 75%. If this is correct, there is an 85% probability that we will observe at least 42 out of 60 participants completing the week-8 assessment.

**Acceptability.** We hypothesize that the true intervention adherence (adoption) rate for the two intervention groups is 70% and 85%, Smoke Sense and Smoke Sense Plus, respectively. If this is correct, there is an 87% probability that we will observe that at least 12 out of 20 participants will adhere to Smoke Sense. There is a 93% probability that we will observe at least 15 out of 20 participants will adhere to or Smoke Sense Plus.

Young adults will be recruited from Washington State University-Spokane, and the Community Colleges of Spokane. (See LOS). Recruitment messages will be posted to social media sites and sent via the respective student affairs offices and health clinics to student list servs. A phone screening will determine study eligibility. If eligible, we will invite participants to the clinical laboratory at WSU Spokane for study visit 1 (Timepoint 1). Research personnel will consent the participant.

Eligible young adults will be randomized with equal probability to 1 of 3 study groups in blocks of 2, 4 and 5. Random assignment of the 60 participants will be determined by [name] using a randomization software. Random group assignment and a corresponding unique study identification (ID) number will be placed in sealed envelopes that are numbered sequentially from 1-60. After the consent is signed, research personnel will open the envelope to reveal the participant's group assignment. Research personnel will record the participant's name, study ID and group assignment in a password protected spreadsheet stored on a secure server at WSU. As part of the training, participants will download the appropriate app to their mobile phones. A set-up macro will ask the participant to enter their study ID which can be associated with all study data captured by the app.

A phone screening will determine study eligibility. If eligible, we will invite participants to the clinical laboratory at WSU Spokane for visit 1 (T1). A research assistant (RA) will consent and randomize the participant but the investigative team will be blinded to group assignment.

Participants will fill out a series of questionnaires via a link sent to their phone. The RA will weigh and measure the participant. The RA will train the participant on the use of a portable digital spirometer with a mouthpiece that connects to the participant's smartphone. The participant will download spirometry software onto their phone and enter their age, sex, height and weight. Participants will be asked to practice exhaling into the mouthpiece. This air turns a motor while the device registers the speed, adapts it and transfers the measurement to the participants' smartphone application. When a participant initiates exhalation, a chronometer changes from red to green after 6 seconds of exhalation. Users can visualize their exhalation curve via the color change and see if they have made an error. The device will select the best result out of 3 attempts. Participants will be asked to return-demonstrate the process until they have definitive results. No calibration is required. Participants will also receive a GPS device and will be instructed on its continuous use during waking hours. Participants will be told that they will be sent an email with a link to a suite of Qualtrics' surveys, which they will be asked to complete via their phone at T2, T3 and T4. Participants in both intervention groups will be instructed on how to download and use the Smoke Sense app. Participants will be asked to return to the clinical lab so research personnel can download their GPS data at T2, T3 and T4. At T4 they will return their spirometer and GPS unit, and complete the System Usability Scale and the Research Attitudes Questionnaire. They can earn \$150, in \$50 increments, per visit, T2-T4.

This study proposes 2 intervention groups: Smoke Sense and Smoke Sense Plus. Smoke Sense Plus offers potentially value-added preventive activities to Smoke Sense. We hypothesize that with these additional activities, users will take actions to reduce their exposure before experiencing symptoms and reduce the severity of outcomes.

Upon downloading, the Smoke Sense mobile app prompts users to set up a Profile, which includes a zip code, demographic information (sex, age, race, education level), baseline health information (pre-existing conditions, physical activity level, time spent outdoors), and beliefs about smoke and air pollution (e.g. Does smoke impact health?). In the Symptoms & Smoke

Observations tab, participants report their weekly observations of smoke, health symptoms, and exposure reduction behaviors. Four symptom categories are reported, eyes and ears, respiratory, cardiovascular, and/or other, as well as the severity of adverse health effects (i.e. symptom duration, whether medication was used, and whether an unplanned trip to a health care provider occurred). In the Fire & Smoke Near Me tab, participants can look at current AQ data measured at monitoring sites and future forecasts. The AQ 101 module leads to trivia games which test knowledge of AQ facts and provides correct answers. Badges are awarded for accomplishments to promote desired behaviors: completing a user profile, launching the app weekly to check local AQ, reporting smoke and symptom observations, expanding AQ knowledge with AQ lessons, and exploring the map. Finally, participants can engage with other users by viewing cumulative statistics of symptoms and smoke observations.

Participants randomized to Smoke Sense Plus will be asked to engage in the Smoke Sense app, as well as additional, evidence-based activities, including: 1) Receive weekly, push notifications that remind them to, for example, review their asthma action plan, take their daily controller medication, refill any expired medications, and identify places to go with filtered indoor air (e.g. library), 2) Monitor lung function daily using a portable spirometer, and 3) Subscribe to a social network to share spirometry data, and exposure reduction strategies. Both interventions will be delivered via participants' smart phones.

The control group will receive incentives for study participation but will not be introduced to the Smoke Sense app.

4.2.b Purpose: PREVENTION

4.2.c Intervention Type: behavioral

IVN Name: Smoke Sense

Description: Smoke Sense is a smartphone application (app). Smoke Sense participants will be asked to establish a profile which includes demographics, baseline health information and current beliefs about smoke and air pollution. In the Symptoms & Smoke Observations tab, participants are asked to report their weekly observations of smoke, health symptoms, and exposure reduction behaviors. In the Fire & Smoke Near Me tab, participants review the most recent AQ data measured at an AQ monitoring sites. Participants are asked to complete the AQ 101 module which test knowledge of AQ facts and provides correct answers. Badges are awarded for accomplishments within the app to promote certain desired behaviors: completing a user profile, launching the app weekly to check local AQ, reporting smoke and symptom observations, expanding AQ knowledge with AQ lessons, and exploring the map. Finally, participants can engage with other users by viewing cumulative statistics of symptoms and smoke observations.

Intervention Type: behavioral

IVN name: Smoke Sense Plus

Description: Participants randomized to the Smoke Sense Plus intervention will be asked to do everything that the Smoke Sense intervention group does on a weekly basis, as well as the following additional activities: 1) Receive weekly push notifications that remind them to, for example, review their asthma action plan, refill any expired medications, take their daily controller medication, identify a clean air space in their home and community, 2) Monitor their lung function weekly via mobile spirometry, and 3) Subscribe to a social network to share strategies to minimize exposure.

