restrictions in range and achievement of MID for each outcome. Generalized linear mixed models (GLMMs) will be fit that include main effects for study group and time point (1=baseline, 2=4 weeks, T3=8 weeks) and the interaction. An identity (continuous outcome) or logit (binary outcome) link function will be specified using SAS 9.4 PROC GLMMIX. Correlations within-participant over repeated measures of time will be controlled for using a random intercept model and a variance component covariate structure. The interaction terms and the slope coefficients for the 3 study groups will be of central interest to characterize changes in each of the outcomes across time. The same analytic approaches will be applied to the secondary (self-report) outcomes including anxiety, exposure reduction behaviors, and mitigating behaviors. Objective measures of exposure reduction behaviors will be estimated using GPS data. To examine the association between each of the GPS-based behaviors and study group during periods of poor AQ, full factorial GLMMs will be fit that include group, day, AQ (1=poor or worse, 0=normal) and specify a random intercept model with an autoregressive covariance structure.

Analyses will examine if the efficacy of the Smoke Sense interventions on outcomes is mediated (adherence to medication therapy, level of self-management skills, and psychological stress) or moderated (asthma severity/control) (Aim 3). For the mediation analyses, PROC CAUSALMED will be used for bootstrapping the CIs of the indirect effects or p-values for the corresponding tests. For moderation by asthma severity/control, we will run the same set of analyses proposed for Aim 2, now including an additional main effect of asthma severity/control and an interaction term of asthma severity/control by study group. We will graph the means of each outcome across subgroups to better understand what, if any, interaction is present. For Aims 2 and 3, two-sided statistical tests will be performed (alpha=0.05). The results from all of the statistical tests performed in Aims 2 and 3 will be interpreted as hypothesis-generating for a future R01 grant submission.

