**Missing data.** If the assumption of “missing at random” can be safely satisfied, GLMM appropriately uses maximum likelihood methods to handle missing data. If this assumption is not satisfied, sensitivity analyses will be performed to examine the impact of different assumptions (e.g. missing not at random) on intervention effects.

**Program Feasibility, Fidelity and Impact.** Program feasibility will be determined by whether or not the rates of recruitment, enrollment, retention in the study (outlined in the Sample Size justification, below) are met. Intervention acceptability will be determined by a high level of engagement with, and adherence to, the Smoke Sense and Smoke Sense Plus interventions. Acceptability of the portable devices used in data collection will be measured using the System Usability Scale, and the Research Attitude Scale.

**Sample Size Justification.** The choice of sample size (n=60) was based on achieving Aim 1, focusing on assessment of the feasibility and acceptability of the Smoke Sense interventions. **Feasibility.** We expect that the true consent rate of eligible young adults is 75%. To test this, we will recruit up to 86 eligible individuals. There is an 89% probability that 60 or more of these individuals will consent to participate if the true consent rate is 75% (based on the cumulative binomial probability). We expect that the true rate of completion of the T3 assessment is 80%. If this is correct, there is an 87% probability that we will observe at least 45 out of 60 participants completing the T3 assessment. Similarly, we expect that the true rate of completion of the T4 assessment is 75%. If this is correct, there is an 85% probability that we will observe at least 42 out of 60 participants completing the T4 assessment. **Acceptability.** We hypothesize that the true intervention adherence rate for the two intervention groups, Smoke Sense and Smoke Sense Plus, is 70% and 85%, respectively. If this is correct, there is an 87% probability that we will observe that at least 12 out of 20 participants will adhere to Smoke Sense. There is a 93% probability that we will observe that at least 15 out of 20 participants will adhere to Smoke Sense Plus.

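### Taken as total sizes, blocks of 2, 4 and 5 cannot balance three arms, so the list of 60 does not guarantee the 20 per arm behind the acceptability probabilities

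*Combined protocol and SAP*

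**What the plan says.** Section 4.2.a gives the allocation rule in one sentence: "Eligible young adults will be randomized with equal probability to 1 of 3 study groups in blocks of 2, 4 and 5". The assignments for all 60 participants are produced in advance by randomization software and "placed in sealed envelopes that are numbered sequentially from 1-60". Once consent is signed, "research personnel will open the envelope to reveal" the group. The section does not say whether 2, 4 and 5 are total block sizes or places per arm. It also does not say how a block that does not divide by three is filled, or that the list is constrained to 20 per arm. Nothing elsewhere in the document describes the blocks.

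The acceptability part of the sample-size reasoning, given in 4.2.a and again in 4.4 (Sample Size Justification), takes 20 participants in each intervention arm. With true adherence of 70% it gives an 87% probability that "at least 12 out of 20 participants will adhere to Smoke Sense". With true adherence of 85% it gives a 93% probability that "at least 15 out of 20 participants will adhere to Smoke Sense Plus".

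Two other statements in 4.4 bear on how much this matters. Acceptability itself is judged loosely: "Intervention acceptability will be determined by a high level of engagement with, and adherence to, the Smoke Sense and Smoke Sense Plus interventions". The Aim 2 and 3 tests "will be interpreted as hypothesis-generating for a future R01 grant submission".

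**The concern.** Permuted blocks keep arm sizes equal only if each block can hold the arms in the intended ratio. For 1:1:1 allocation the total block size must be a multiple of 3. Read in the usual way, as totals, 2, 4 and 5 all fail this, and a block of 2 cannot even contain every arm. Whoever generates or audits the list has to invent a rule for the extra places, and different rules give different degrees of imbalance.

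At stake is the match between the allocation rule and the acceptability probabilities, which hold only for arms of exactly 20. The sample size of 60 is justified by Aim 1, so 20 per arm is part of that justification. The validity of the group comparisons is not at stake.

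**Working it through.** **Inputs.** From 4.2.a: three arms with equal probability, block sizes 2, 4 and 5, and 60 envelopes. From 4.2.a and 4.4: adherence of 70% and 85%, counts of at least 12 and at least 15, and 20 per intervention arm.

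**1. The plan's own figures.** With X binomial (n, p), the upper tail at n = 20 is:
- P(X ≥ 12 | 20, 0.70) = 0.887, against 87% stated
- P(X ≥ 15 | 20, 0.85) = 0.933, against 93% stated

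The second agrees. The first is 1.7 points above the stated value, a small difference unrelated to this point.

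**2. Divisibility.** 2 = 3×0 + 2; 4 = 3×1 + 1; 5 = 3×1 + 2. The remainders are 2, 1 and 2, so no block is balanced.

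**3. Arm sizes on the total-size reading.** The plan gives no fill rule, so I assume one: sizes are drawn at random, each block of size b gives floor(b/3) places to every arm, the leftover places go to distinct random arms, and the list is cut at 60. The second row changes only the leftover rule. The unblocked row is for comparison; its SD is √(60 × 1/3 × 2/3) = 3.65. All rows are simulated (40,000 to 60,000 lists each).

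| Scheme | P(20/20/20) | SD per arm | P(a given arm has 18–22) |
|---|---|---|---|
| 2/4/5, leftovers to distinct arms | 0.049 | 1.95 | 0.803 |
| 2/4/5, leftovers drawn independently | 0.029 | 2.49 | 0.686 |
| Unblocked 1:1:1 | 0.014 | 3.65 | – |

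In the first row, all three arms have 18 to 22 in 0.602 of lists, and the largest and smallest arms differ by 4 or more in 0.541. A separate run of 200,000 lists gave 0.048 for 20/20/20 and an SD of 1.94.

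**4. What arm size does to the probabilities.** The plan does not say whether 12 and 15 are fixed counts or stand for 60% (12/20) and 75% (15/20), so both readings are shown. On the proportional reading the required count is rounded up; for n = 18, 0.60 × 18 = 10.8 becomes 11 and 0.75 × 18 = 13.5 becomes 14.

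| n | Counts held: ≥12 at 70% | Counts held: ≥15 at 85% | ≥60% at 70% | ≥75% at 85% |
|---|---|---|---|---|
| 18 | 0.722 | 0.720 | 0.859 | 0.879 |
| 19 | 0.818 | 0.856 | 0.818 | 0.856 |
| 20 | 0.887 | 0.933 | 0.887 | 0.933 |
| 21 | 0.932 | 0.971 | 0.852 | 0.917 |
| 22 | 0.961 | 0.989 | 0.814 | 0.900 |

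Averaged over the arm sizes in step 3 (first row), the two probabilities are about 0.85 and 0.86 with counts held, and about 0.85 and 0.90 as proportions. The joint probability with counts held is about 0.72, against 0.8867 × 0.9327 = 0.827 at 20 per arm.

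**5. Places-per-arm reading.** Multiplying by three arms gives total sizes 6, 12 and 15, and every complete block balances. Randomly ordered blocks end exactly at 60 in only about 27% of lists. With the list cut at 60, 20/20/20 arises in 0.469, the SD is 0.68, and a given arm has 18 to 22 in over 99.9%. The joint probability with counts held is 0.814 against 0.827.

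**6. Blocks that work.** Multiples of 3 are not enough if the list is simply cut at 60: 20/20/20 then arises in 0.799 of lists with blocks of 3 and 6, and in 0.607 with blocks of 6 and 9. A sequence constrained to sum to 60 gives it always, for example 4×6 + 4×9 = 60 or 6 + 12 + 12 + 15 + 15 = 60.

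**The case against.** The strongest reply is that the defect is conditional. The sentence may mean places per arm, in which case the effect is negligible. Even on the total-size reading, the 5% depends on a fill rule that the plan does not state. The list is generated before enrolment, so its totals could be set or checked at 20 each, and the plan clearly expects 20 per intervention arm. Holding 12 and 15 fixed as an arm shrinks is also the harsher convention for small arms: read as proportions, an arm of 18 gives 0.859 and 0.879, not 0.722 and 0.720. Finally, the stated blocks still hold the SD to about half that of unblocked allocation (1.95 against 3.65).

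Much of this stands, and it limits the size of the point. The 5% illustrates one plausible fill rule and is not a property of the plan; the proportional reading does soften the loss. What does not fall is the arithmetic: the sizes as written do not divide by three, and neither a fill rule nor a constraint to 20 per arm is stated. The places-per-arm reading has to be supplied by the reader, and even then the blocks must be chosen to sum to 60.

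**Conclusion.** The concern holds as a minor one. Read as total sizes, the stated blocks cannot balance three arms, so the list does not guarantee the 20 per arm used in the acceptability probabilities. Under the assumed fill rule, exact balance arises in about 5% of lists, the SD of an arm's size is about 1.9 to 2.0, and the average loss in the two probabilities is about 4 and 7 points with counts held (0.887 to 0.85; 0.933 to 0.86), or about 4 and 3 points as proportions (0.887 to 0.85; 0.933 to 0.90). On the places-per-arm reading the loss is negligible.

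The consequence is modest. The counts 12 and 15 are not fixed pass marks, allocation remains random with equal expected arm sizes, the Aim 2 and 3 tests are exploratory, and the recruitment and retention probabilities use totals that the arm split does not touch.

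**What to change.** In 4.2.a, replace "in blocks of 2, 4 and 5" with total block sizes that are multiples of 3, each balanced 1:1:1, in a randomly ordered sequence constrained to sum to 60, so that each arm has 20. Sizes 3 and 6 would satisfy the arithmetic. Sizes 6 and 9 (four of each) are preferable if small blocks are thought too predictable, since the last place in a block of 3 is known to anyone who infers the size. Keep the block sizes from the staff who open the envelopes.

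If 2, 4 and 5 were meant as places per arm, state the sizes as 6, 12 and 15 and use a sequence that sums to 60, such as 6, 12, 12, 15 and 15 in random order.

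If enrolment has begun (the document does not say), balanced blocks for the unopened envelopes limit further imbalance but cannot restore 20 per arm if the opened ones are already unequal. In that case, or if the list is kept, report the actual arm sizes and recalculate the acceptability probabilities for them.

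The cost is one sentence in the protocol and a regenerated list, or its unopened part. No extra participants, visits or staff are needed.

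### As written, nothing keeps the T1 baseline measures from being taken after the allocation envelope is opened, so baseline is not protected from knowledge of the arm

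*Combined protocol and SAP*

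**What the plan says.** All of the visit 1 (T1) procedure is in section 4.2.a of the combined protocol and SAP.

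- **Trigger for allocation.** "After the consent is signed, research personnel will open the envelope to reveal the" participant's arm. No baseline measurement is named as a precondition. The sealed envelope holds both the group and the study ID.
- **Who learns the group.** "Research personnel will record the participant's name, study ID and group assignment in a password protected spreadsheet". Further on: "A research assistant (RA) will consent and randomize the participant but the investigative team will be blinded to group assignment".
- **What is described next.** "Participants will fill out a series of questionnaires via a link sent to their phone". The RA then takes height and weight, and after that: "The RA will train the participant on the use of a portable digital spirometer with a mouthpiece that connects to the participant's smartphone". The manoeuvre is repeated: "Participants will be asked to return-demonstrate the process until they have definitive results". The GPS device follows, and Smoke Sense instruction for the two intervention groups comes later still.

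Section 4.2.f lists masking of the investigator only. Section 4.4 (analytic plan) fits mixed models with group, time point and their interaction. Baseline is time point 1, and the interaction terms and group slopes are the quantities of main interest.

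**The concern.** Baseline is useful in a randomized comparison because it cannot have been influenced by the assignment. That holds only if it is measured before anyone involved in the measurement knows the arm, or if the measurement cannot respond to that knowledge. Here several of the outcomes can respond. The Asthma Control Test (ACT), quality of life and anxiety are self-reported. Spirometry depends on effort and is taught by the person who randomized the participant. Home spirometry is also one of the added activities in Smoke Sense Plus, so an RA who knows the arm has a reason, even without intending it, to teach it differently.

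What is at stake is the Aim 2 estimate of effect. Sections 4.1 and 4.2.a say that the effect size and its variance are wanted for planning a later trial, so a distortion at baseline would be carried into that planning. No analysis can recover an uncontaminated baseline afterwards.

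**Working it through.** No figure in the plan depends on the order of the T1 steps, so there is none to reproduce. The check is to trace the steps and then see how a baseline shift passes through the planned model.

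**Step 1: order of procedures (section 4.2.a; masking from 4.2.f).**

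| Step in the text | Is the arm known? |
|---|---|
| Consent signed | No |
| Envelope opened, group recorded by research personnel | RA: yes, explicit. Participant: probably, inferred from disclosure at the visit and investigator-only masking |
| Questionnaires on the participant's phone | As above |
| Height and weight, spirometer training and repeated attempts | As above |
| Smoke Sense instruction, intervention groups | Participant certainly knows by this step |

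Two separate statements, the envelope sentence and the one giving the RA both consent and randomization, put allocation next to consent. No sentence puts a T1 measurement before it.

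**Step 2: effect on the contrast.** Let D be the true difference in change from baseline to week 8, intervention minus control:

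D = (Y8,int - Y0,int) - (Y8,con - Y0,con).

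If knowledge of the arm shifts the intervention baseline by x and the week-8 value by y, the plan estimates

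D* = D + y - x.

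- Shift at baseline only (y = 0): D* = D - x, one-for-one with opposite sign.
- Shift persisting equally (y = x): D* = D, so it cancels.

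The same holds for a linear slope over three equally spaced visits with complete data. The slope is (Y3 - Y1)/2 per interval, so a baseline-only shift changes it by -x/2 per interval, or -x over the two intervals.

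**Step 3: scale.** Section 4.3 gives 3 points as the minimally important difference (MID) for ACT. The documents give no value for x. For assumed shifts:

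- x = 0.5: 0.5/3 = 17% of the MID
- x = 1.0: 1.0/3 = 33% of the MID

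**Step 4: check in the planned type of model.** A random-intercept model with group, time and interaction was simulated with two arms of 20, no true effect, and 100 runs per setting. The between-person SD of 3 and residual SD of 2 are assumptions. Baseline was lowered in one arm only, so the expected interaction is positive.

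| Baseline lowered by | Mean group-by-week-8 interaction | Monte Carlo SE |
|---|---|---|
| 0 | -0.09 | 0.08 |
| 0.5 | 0.64 | 0.09 |
| 1.0 | 1.16 | 0.09 |
| 1.5 | 1.50 | 0.10 |

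Each mean lies within two standard errors of the imposed shift, which agrees with the algebra. The simulation assumes a baseline-only shift. It shows how such a shift would pass through the model and is no evidence that one would occur.

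**The case against.** The strongest reply is that the order is read into the text. Consent is a necessary condition for opening the envelope, and the plan does not say that opening follows at once. The narrative is also not strictly chronological: after the envelope and app download it starts again with the phone screening. No sentence says when the participant is told the arm. This stands as a limit on certainty. It does not remove the point, because the plan contains nothing that would stop staff from opening the envelope first, and its plain reading leads them to do so.

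The scope for influence is also limited. Participants complete the questionnaires themselves on their phones, ACT asks about the previous four weeks, and the device keeps the best of three attempts. The T1 spirometry is described as training and practice; that it supplies the analysed baseline is an inference from baseline being time point 1. These facts make a large shift less likely but do not exclude one. Follow-up self-report is unmasked too, so part or all of a persistent shift would cancel. That also stands.

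Aims 2 and 3 are labelled hypothesis-generating, and the sample size rests on Aim 1, whose rates this ordering hardly touches. This lowers the stakes, but the change is nearly free.

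A reader might infer two stronger points that the documents do not support:

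- **That baseline becomes an invalid adjustment variable.** The Aim 2 model in section 4.4 treats baseline as a repeated outcome and specifies no baseline covariate.
- **That participants who cannot produce a usable spirometry result are lost after randomization and depress retention.** No section withdraws or excludes them; they repeat the manoeuvre. How well the portable devices work is itself part of Aim 1.

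**Conclusion.** The point holds as a weakness in the written procedure. Signed consent is the only stated condition for revealing allocation, the RA who randomizes also teaches the spirometry, and no section protects the T1 measures from knowledge of the arm. The RA's knowledge is explicit; the participant's is probable but inferred.

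The consequence is conditional. A between-arm shift confined to baseline enters the difference in change in full with the opposite sign, and one that persists equally does not enter at all. The size is unknown. The 17% to 33% of the ACT MID rests wholly on an assumed shift of 0.5 to 1 point, and should not be read as an estimate of bias in this trial. The sponsor should make the change because it removes a possible source of bias at almost no cost. If staff already complete baseline first, the plan should say so.

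**What to change.** In section 4.2.a, replace consent as the trigger. State that the envelope is opened only after the T1 questionnaires, height and weight, and baseline spirometry are completed, and that app download and arm-specific training come last in the visit. State also that the T1 spirometry result is the baseline value, if that is intended.

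Reordering alone is not enough. The study ID is sealed with the allocation, so baseline data could not be labelled until the envelope is opened. Take the ID out of the sealed contents, for example by printing it on the outside of the sequentially numbered envelope.

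The cost is re-preparing 60 envelopes and revising the visit order. No measurement, visit or staff member is added.
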